5. STUDY ASSESSMENTS AND PROCEDURES

A window of -2 / +3 days can be applied to scheduled visits for nivolumab and ipilimumab administration if necessary for holidays, vacations, inclement weather, etc.

5.1. Screening Period

The following procedures and tests will be completed during this period to determine eligibility. All procedures to be completed within 28 days of first dose, except labs. All labs should be collected within 14 days of first dose.

- 1) History and physical examination
- 2) Measurement of height, weight and vital signs (including blood pressure, heart rate, respiratory rate, oxygen saturation, and temperature).
- 3) Performance status evaluation
- 4) CBC with differential, serum chemistry (Na, K, Cl, CO₂, BUN, creatinine, glucose, calcium), magnesium, phosphate, amylase, lipase, liver function tests (albumin, total protein, alkaline phosphatase, total bilirubin, ALT, AST), LDH, TSH (with reflex to free T3 and free T4)
- 5) Pregnancy test (serum or urine) for women of childbearing potential. Sexually active women of childbearing potential must use an effective method of birth control during the course of the study, in a manner such that risk of failure is minimized.
- 6) Systemic tumor assessment with CT scan of the chest/abdomen/pelvis and CT or MRI Brain (MRI preferable). MRI brain required only if known or suspected brain metastases.

If eligible, a tumor biopsy and blood draw for research studies (approximately 2 tablespoons of blood) will be performed prior to initiation of therapy (see section 4.1.1).

5.2. On-Study Visits

The day of the nivolumab infusion (every 2 weeks) and the day of the ipilimumab infusion (every

6 weeks):

- 1) History and physical examination
- 2) Measurement of height, weight and vital signs (including blood pressure, heart rate, respiratory rate, oxygen saturation, and temperature).
- 3) Performance status evaluation
- 4) Review concomitant medications
- 5) Adverse events assessment
- 6) CBC with differential, serum chemistry (Na, K, Cl, CO₂, BUN, creatinine, glucose, calcium), magnesium, phosphate, liver function tests (albumin, total protein, alkaline phosphatase, total and, ALT, AST), LDH
- 7) Pregnancy test (serum or urine) for women of childbearing potential (every 6 weeks)
- 8) Administration of nivolumab and/or ipilimumab accordingly.
- 9) TSH with reflex free T4 and free T3 (every 6 weeks)

Tumor response assessment will occur every 9 weeks after initiating trial therapy for the first 24 weeks, and thereafter every 12 weeks.

Tumor biopsies (excision, core or forceps) will be performed 9 to 10 weeks after initiating trial therapy after the 4th or 5th nivolumab infusion to allow for analysis of pharmacodynamics changes related to trial therapy (see Sections 4.1.1 and 7). Blood will be drawn for correlative studies the day of the first four nivolumab infusions, and the week after the 5th nivolumab infusion.

5.3. Follow-up Visits

All patients who discontinue the study treatment will have a follow up visit at Day 28 ±7 days from the last study treatment.

- 1) History and physical examination
- 2) Measurement of height, weight and vital signs (including blood pressure, heart rate, respiratory rate, oxygen saturation, and temperature).
- 3) Performance status evaluation
- 4) Review concomitant medications
- 5) Adverse events assessment
- 6) CBC with differential, serum chemistry (Na, K, Cl, CO₂, BUN, creatinine, glucose, calcium), magnesium, phosphate, liver function tests (albumin, total protein, alkaline phosphatase, total, ALT, AST), LDH, and TSH with reflex free T4 and free T3
- 7) Tumor assessment with CT scan of the chest/abdomen/pelvis and brain every 9 weeks (+/- 5 days) until progression, withdrawal of consent, death, lost to follow-up, or start of a subsequent anti-cancer therapy

All patients who discontinue early or who complete the study treatment period will be followed for survival. Survival follow-up information will be collected via telephone calls, patient medical records, and/ or clinic visits every 3 months +/- 14 days until death, loss to follow-up or study termination. All patients will be followed for survival unless the patient requests to be withdrawn from follow-up. If the patient withdraws from study treatment but not from follow-up, the study staff may use a public information source to obtain information about survival status.

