| 
 b. No ongoing requirement for dexamethasone as therapy for CNS disease; anticonvulsants at a stable dose are allowed. c. Completed stereotactic radiosurgery at least 1 week prior to Cycle 1, Day 1 or whole-brain radiation at least 2 weeks prior to Cycle 1, Day 1. - History of leptomeningeal carcinomatosis - Prior palliative radiotherapy outside the CNS within 2 weeks of the first dose of study drug - Treatment with systemic immunosuppressive medications (including but not limited to, dexamethasone at doses > 2 mg daily (or equivalent dose of other corticosteroids), cyclophosphamide, tacrolimus, sirolimus, azathioprine, methotrexate, thalidomide, and antitumor necrosis factor [anti-TNF] agents) within 2 weeks prior to initiating trial therapy (Inhaled or topically applied steroids, and acute and chronic standard-dose NSAIDs are permitted. Replacement steroids are also permitted). |
| 
Intervention and Mode of Delivery:
 
Nivolumab 3 mg/kg IV every 2 weeks and Ipilimumab 1 mg/kg IV every 6 weeks
 |
| 
Duration of Intervention and Evaluation:
 
Combination therapy with ipilimumab and nivolumab will be continued until disease progression or unacceptable toxicity. Patients with progression of disease by RECIST v1.1 without decline in performance status will be allowed to continue trial therapy if their treating physician believes they are deriving clinical benefit from study therapy.
 
Both RECIST v1.1 and immune-related response criteria (irRC) will be used to assess response to therapy. All patients who receive at least one dose each of ipilimumab and nivolumab will be considered evaluable.
 
Tumor response will be based on tumor assessments at screening, every 9 weeks from the first dose (for the first 24 weeks) and thereafter every 12 weeks until investigator-assessed initial disease progression.
 |

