4.3.1. Dose Delay Criteria

Dose delay criteria apply to all drug-related AEs. Treatment delays are allowable up to 6 weeks for nivolumab and 12 weeks for ipilimumab from the last dose (any dose delays greater than this will require approval from the medical monitor).

Tumor assessments for all subjects should continue as per protocol **even if dosing is delayed**.

Nivolumab and ipilimumab administration should be delayed for the following:

- Grade 2 non-skin, drug-related adverse event, except for fatigue and laboratory abnormalities
- Grade 2 drug-related creatinine, AST, ALT and/or Total Bilirubin abnormalities
- Grade 3 skin, drug-related AE
- Grade 3 drug-related laboratory abnormality with the following exceptions:
 - Grade 3 lymphopenia or asymptomatic amylase or lipase elevation does not require dose delay
 - Grade ≥ 3 AST, ALT, Total Bilirubin will require dose discontinuation
 - Any AE, laboratory abnormality or intercurrent illness which, in the judgment of the investigator, warrants delaying the dose of study medication.

Participants who have drug-related toxicities that meet the criteria for dose delay should have both drugs (ipilimumab and nivolumab) delayed until retreatment criteria are met. (Exceptions apply to the retreatment criteria after dose delay of ipilimumab and nivolumab for Grade ≥ 3 amylase and lipase abnormalities that are not associated with symptoms or clinical manifestations of pancreatitis and that are attributed to ipilimumab alone.)

Rescheduling:

Nivolumab may be delayed until the next planned ipilimumab dose if the next ipilimumab dose is scheduled within the next 12 days. This will permit periodic ipilimumab dosing to be synchronized with nivolumab dosing.

Ipilimumab should be dosed at the specified interval regardless of any delays in intervening nivolumab doses. However, in order to maintain periodic synchronized dosing of ipilimumab and nivolumab, the dosing days of nivolumab (every 2 weeks ± 3 days) and ipilimumab (every 6 weeks ± 5 days) may be adjusted within the permitted ± 5 day window, as long as consecutive nivolumab doses are given at least 12 days apart. Ipilimumab may be delayed beyond the 5 day window if needed to synchronize with the next nivolumab dose.

If an ipilimumab dose is delayed beyond 6 weeks from the prior ipilimumab dose, then subsequent ipilimumab doses should be rescheduled to maintain the 6 week interval between consecutive ipilimumab doses.

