8. CRITERIA FOR RESPONSE

Anti-tumor activity: data on objective response, progression free survival, and duration of response will be listed for all patients in the study and summarized overall.

Objective response is defined as a complete or partial response, as determined by investigator assessment using RECIST v1.1 and irRC (see appendix 3 and 4) and confirmed by repeat assessments ≥ 4 weeks after initial documentation. Patients not meeting these criteria, including patients without any post baseline tumor assessment, will be considered non-responders in the analysis of objective response.

Duration of objective response will be analyzed for the subset of patients who achieved an objective response. Duration of response is defined as the time from the initial complete or partial response to the time of disease progression or death, whichever occurs first. If a patient does not experience death or disease progression before the end of the study, duration of response will be censored at the day of the last tumor assessment. If no tumor assessments were performed after the date of the first occurrence of a complete or partial response, duration of objective response will be censored at the date of the first occurrence of a complete or partial response plus 1 day.

Progression-free survival is defined as the time from the first day of nivolumab treatment until progression of disease using RECIST v1.1 and irRC (see appendix 3 and 4). If a patient has not experienced progressive disease or death, PFS will be censored at the day of the last tumor assessment. Patients with no post baseline tumor assessments will be censored at the date of first study treatment plus 1 day.

[figure not shown]
Overall survival is defined as the time from the first day of treatment until death from any cause. If a patient has not experienced death, OS will be censored at the day of last follow-up.

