9. STATISTICAL CONSIDERATIONS

This trial is designed to determine the objective response rate (ORR) using RECIST v1.1 and irRC to nivolumab and ipilimumab when administered in combination to patients with advanced NSCLC and primary resistance to PD-1 axis inhibitor therapy. Details on the response criteria and its duration are described in Section 8 of this protocol. For our primary endpoint we will employ a Simon two-stage design. This design is based on our intuition for a very low response rate and not on any specific experimental evidence. The study design will terminate early if there are no responses or prolonged stability (≥ 24 weeks) using irRC among the first 10 patients enrolled. Otherwise we will enroll a maximum of 40 and reject the null hypothesis if we observe 4 or more

positive responses. For a null hypothesis with a 5% ORR and alternative with a 19% ORR, this criterion has significance level 0.1 and power greater than 85%. The null and alternative hypothesis rates are not motivated by experimental evidence but rather, are examples of one pair of hypotheses that can be tested using this design.

An operating characteristic of this design with other ORRs is plotted here:

We anticipate enrollment at a rate of at least 2 patients per month. Patients who drop out or leave the study before receiving any experimental treatment will be replaced. Patients who leave the study after receiving any study treatment will be considered as treatment failures and not be replaced.

Our secondary analyses correlate ORR, time-to-event measures and correlative metrics listed in Section 7. Specifically, duration of response, progression-free survival (PFS) and overall survival (OS) will be estimated along with the corresponding 95% CI, plotted using the Kaplan-Meier method. These plots will also be prepared separately by RECIST v 1.1 criteria and irRC and tested using the log-rank test. Duration of response, OS, and PFS are defined in Section 8.

Marker data and other metrics listed in Section 7 will be correlated to ORR and PFS using Cox proportional hazard regression methods. These values will be analyzed marginally using heatmaps and single linkage to identify any subpopulations.

The following analysis sets will be defined in this trial:

- Full Analysis Set: All subjects who receive at least 1 dose of any trial treatment.

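### Section 5.3 sets 9-week scans with no start point after treatment stops, which contradicts the synopsis's single schedule from first dose; the likely effect on PFS is very small

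*Combined protocol and SAP*

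**What the plan says.** Four places in the combined protocol and SAP set the timing of tumor assessments.

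- **Synopsis, Duration of Intervention and Evaluation:** scans are "every 9 weeks from the first dose (for the first 24 weeks) and thereafter every 12 weeks until investigator-assessed initial disease progression". Nothing ties this to being on treatment.
- **Section 5.2 (On-Study Visits):** "Tumor response assessment will occur every 9 weeks after initiating trial therapy for the first 24 weeks, and thereafter every 12 weeks".
- **Section 5.4 (Study Calendar):** imaging at week 9, at week 18, and every 12 weeks from there. The end-of-treatment column shows no imaging entry.
- **Section 5.3 (Follow-up Visits), for patients who have stopped treatment:** "every 9 weeks (+/- 5 days) until progression, withdrawal of consent, death, lost to follow-up, or start of a subsequent anti-cancer therapy". The interval never lengthens and no start point is given.

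Section 4.3.1 adds that during a dose delay "Tumor assessments for all subjects should continue as per protocol", so a delay alone does not change the timing.

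Two secondary measures depend on the progression date. Section 8 states: "Progression-free survival is defined as the time from the first day of nivolumab treatment until progression of disease using RECIST v1.1 and irRC". Without an event, "PFS will be censored at the day of the last tumor assessment". It also states: "Duration of response is defined as the time from the initial complete or partial response to the time of disease progression or death". Under Section 9, "duration of response, progression-free survival (PFS) and overall survival (OS) will be estimated along with the corresponding 95% CI", by Kaplan-Meier. Neither section has a rule or sensitivity analysis for unequal scan intervals.

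**The concern.** A patient who stops for toxicity after week 24, without progression, falls under two instructions. The synopsis keeps that patient on 12-week scans counted from first dose. Section 5.3 moves the patient to 9-week scans, which could be counted from first dose, last dose, the day-28 follow-up visit or the last scan. Different staff could schedule the same patient differently and each be following the protocol.

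If Section 5.3 is followed, the scan interval changes because of something that happens after baseline. Progression is dated to the scan that shows it, so two patients with the same disease course can get different progression dates because one is off treatment. PFS and duration of response are both built on that date.

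**Working it through.** The plan states no sample size, event count or power for PFS or duration of response, so there is no figure of its own to reproduce.

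**1. Scan weeks.** Calendar: 9, 18, 30, 42, 54, and so on. A 9-week count, taken here from first dose because Section 5.3 gives no start: 9, 18, 27, 36, 45, 54. The first difference is week 27 against week 30. The pattern repeats every 36 weeks, so weeks 18 to 54 cover one full cycle.

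| True progression (weeks) | Calendar date | 9-week date | Off-treatment date is |
|---|---|---|---|
| 18–27 (9 weeks) | 30 | 27 | 3 weeks earlier |
| 27–30 (3 weeks) | 30 | 36 | 6 weeks later |
| 30–36 (6 weeks) | 42 | 36 | 6 weeks earlier |
| 36–42 (6 weeks) | 42 | 45 | 3 weeks later |
| 42–45 (3 weeks) | 54 | 45 | 9 weeks earlier |
| 45–54 (9 weeks) | 54 | 54 | the same |

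For progression spread evenly over the cycle, the mean is (9×3 − 3×6 + 6×6 − 6×3 + 3×9 + 9×0)/36 = 54/36 = 1.5 weeks earlier. The off-treatment date is earlier for 9 + 6 + 3 = 18 of the 36 weeks, later for 3 + 6 = 9, and the same for 9.

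**2. Mean detection delay.** With exponential PFS at rate λ = ln 2/median and scan interval L, the mean delay is L/(1 − exp(−λL)) − 1/λ. The medians are assumptions taken from the first-line trial in Table 2.2.2, at 4.348 weeks per month.

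- Median 3.9 months (λ = 0.0409 per week): 4.78 weeks for L = 9 and 6.49 weeks for L = 12.
- Median 8.1 months (λ = 0.0197 per week): 4.63 weeks for L = 9 and 6.24 weeks for L = 12.

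Both schedules date progression late. The 9-week schedule is on average less late, by 1.6 to 1.7 weeks.

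**3. Effect on the cohort.** One million patients per scenario were simulated with exponential PFS and a toxicity stop at a uniform time over weeks 0 to 52, which counts only if it precedes progression. The share assigned a stop is 13% (Table 2.2.1, every-6-week ipilimumab arm) or an assumed 30%; 100% is an extreme. The shift is mean observed PFS on the calendar schedule for everyone minus that on the mixed schedule.

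| Median PFS | Assigned a stop | Stop before progression | Shift in mean PFS | Observed median |
|---|---|---|---|---|
| 3.9 months | 13% | 5.4% | 0.07 weeks | 18 weeks, unchanged |
| 3.9 months | 30% | 12.4% | 0.16 weeks | 18 weeks, unchanged |
| 8.1 months | 13% | 8.1% | 0.12 weeks | 42 weeks, unchanged |
| 8.1 months | 30% | 18.8% | 0.27 weeks | 42 weeks, unchanged |
| 3.9 months | 100% | 41.3% | 0.53 weeks | 18 weeks, unchanged |
| 8.1 months | 100% | 62.6% | 0.89 weeks | 42 weeks, unchanged |

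Counting the 9 weeks from the last on-treatment scan instead of first dose gives the same results to within 0.01 weeks.

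**4. Duration of response.** This was not simulated. At the response rates in Section 9, 40 patients give 40 × 0.05 = 2 to 40 × 0.19 = 7.6 responders. At 13% stopping, 0.13 × 2 = 0.26 to 0.13 × 7.6 = 0.99 responders would be affected.

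**The case against.** The strongest reply is that this is a wording slip with no practical effect on the results. The trial has a single arm, PFS and duration of response are secondary, and no planned analysis compares patients by treatment status. Patients who stop because of progression, who progress by week 18, or who only have a dose delay are unaffected. The mean shift of 0.07 to 0.27 weeks is about 0.5 to 1.9 days (0.07 × 7 and 0.27 × 7), which is within the 5-day scan window of Section 5.3 itself. All of that stands, and it limits the point to a minor one.

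It could also be said that Section 5.3 only adds detail to a summary in the synopsis. That does not resolve the matter: after week 24 the two give different intervals for the same patient, and only the synopsis states a start point.

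A reader might go further and infer that the schedule materially biases PFS, that progression is always found sooner off treatment, or that the gap is at most the 3 weeks between the two intervals. The documents support none of these. The cohort shift is very small. The off-treatment date is earlier in only half of the 36-week cycle, and individual differences reach 9 weeks one way and 6 weeks the other.

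Nor do the documents support a threat to the primary endpoint. That is response rate, and the final decision counts responses. The first-stage rule also counts stability of at least 24 weeks by irRC, but how this is dated is not defined and no effect on it was sized, so nothing is claimed about it here.

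**Conclusion.** The contradiction is real and must be reconciled. The synopsis gives one schedule from first dose until progression, Section 5.2 and the calendar use the same intervals, and Section 5.3 departs from them for patients off treatment without giving a start point. If Section 5.3 is followed, recorded progression dates after about weeks 18 to 24 depend on treatment status.

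The size is small. The 1.5-week average and the individual range follow from the calendar weeks and a 9-week count from first dose; another start point would change the individual differences. The cohort figures rest on exponential PFS, on medians of 3.9 and 8.1 months and on 13% to 30% assigned a toxicity stop. The medians and the 13% come from a first-line trial, not from patients resistant to anti-PD-1 therapy; the 30% is an assumed upper value.

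Duration of response is the more exposed measure, because one responder dated a scan earlier or later could move a median based on so few. That effect is possible but was not quantified.

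**What to change.** Reconcile the synopsis and Sections 5.2, 5.3 and 5.4 into one tumor assessment schedule. It should be counted from the first dose and applied regardless of treatment status until progression or new anti-cancer therapy, with the same wording in all four places. The synopsis already contains wording of this kind. With one schedule for everyone, the difference by treatment status is zero by construction.

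The cost is about one line in Section 5.3. If the synopsis intervals are kept, patients off treatment have slightly fewer scans after week 24.

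For any patients already scanned on differing schedules, an interval-censored sensitivity analysis of PFS and duration of response would deal with the dating. It would not remove the contradiction in the text.

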5.4. STUDY CALENDAR

| W (week) | Pre-Tx | W 1 | W 2 | W 3 | W 4 | W 5 | W 6 | W 7 | W 8 | W 9 | W 10 | W 11 | W 12 | W 13 | W 14 | W 15 | W 16 | W 17 & Q2W | End of Tx |
|------------------------------|--------|-----|-----|-----|-----|-----|-----|-----|-----|-----|------|------|------|------|------|------|------|-------------|------------|
| Nivolumab | | X | | X | | X | | X | | X | | X | | X | | X | | X | |
| Ipilimumab | | X | | | | | | X | | | | | | X | | | | | W 19 & Q6W |
| Informed Consent | X | | | | | | | | | | | | | | | | | | |
| Demographics | X | | | | | | | | | | | | | | | | | | |
| Medical History | X | | | | | | | | | | | | | | | | | | |
| Concurrent Meds | X | X | | X | | X | | X | | X | | X | | X | | X | | X | X |
| Physical Exam | X | X | | X | | X | | X | | X | | X | | X | | X | | X | X |
| Vital Signs ¹ | X | X | | X | | X | | X | | X | | X | | X | | X | | X | X |
| Height | X | | | | | | | | | | | | | | | | | | |
| Weight | X | X | | X | | X | | X | | X | | X | | X | | X | | X | X |
| ECOG PS | X | X | | X | | X | | X | | X | | X | | X | | X | | X | X |
| CBC w/diff, plts | X | X | | X | | X | | X | | X | | X | | X | | X | | X | X |
| Serum chemistry ² | X | X | | X | | X | | X | | X | | X | | X | | X | | X | X |
| TSH ³ | X | | | | | | | X | | | | | | X | | | | W 19 & Q6W | X |
| Amylase/ Lipase | X | | | | | | | | | | | | | | | | | | X |
| B-HCG ⁴ | X | | | | | | | X | | | | | | X | | | | W 19 & Q6W | X |
| EKG | X | | | | | | | | | | | | | | | | | | |
| Adverse Event Evaluation | X | X | | X | | X | | X | | X | | X | | X | | X | | X | X |
| Trial Imaging | X | | | | | | | | | X | | | | | | | | W 18 & Q12W | |
| Tumor Biopsy | X | | | | | | | | | | X | | | | | | | | |
| PD Blood Draw | X | X | | X | | X | | X | | | X | | | | | | | | X |

1. Includes blood pressure, heart rate, respiratory rate, oxygen saturation, and temperature
2. Albumin, alkaline phosphatase, total bilirubin, bicarbonate, BUN, calcium, chloride, creatinine, glucose, LDH, phosphorus, potassium, total protein, SGOT [AST], SGPT [ALT], sodium.
3. Reflex to Free T3 and T4 is TSH abnormal
4. Serum or urine pregnancy test (women of childbearing potential)
5. All screening procedures except labs to occur within 28 days of first dose. All labs to be collected within 14 days of first dose.

